## 11.2 Clinical Laboratory Variables

Descriptive statistics for clinical laboratory values (in SI units) and changes from baseline at each assessment time point as well as shift tables from baseline to each visit for quantitative variables will be presented by treatment for the following clinical laboratory variables.

**Hematology** Hemoglobin, hematocrit, red blood cells (RBC), platelet count, white blood cell count – total and differential (WBC), total neutrophils, lymphocytes, monocytes, eosinophils, basophils.

**Biochemistry** Sodium, potassium, glucose, blood urea nitrogen, creatinine, calcium, chloride, thyroid stimulating hormone (TSH)a, thyroxine (T4 total)a, triiodothyronine (T3)a, 25(OH)Da, phosphorus, total protein, total CO2 (Bicarbonate), albumin, aspartate transaminase, alanine transaminase, gamma glutamyl transferase, alkaline phosphatase, total bilirubin, uric acid, Creatinine clearancea, β-HCGb, FSHb, Magnesium.

β-HCG=beta-human chorionic gonadotropin; FSH=follicle stimulating hormone; T3=triiodothyronine; TSH=thyroid stimulating hormone

a Tests done at Screening only and therefore will not appear in summary tables. They will be listed.

b Females only.

**Urinalysis** Glucose, specific gravity, blood, ketones, protein, calcium, bilirubin, pH, leukocyte esterase, and nitrites.

Clinical laboratory test values are potentially clinically important (PCI) if they meet either the low or high PCI criteria listed in Table 5. The number and percentage of subjects with post-baseline PCI values will be tabulated by treatment. The percentages will be calculated relative to the number of subjects with available baseline values and at least 1 post-baseline assessment. The numerator is the total number of subjects with at least 1 post-baseline PCI value. A supportive listing of subjects with post-baseline PCI values will be provided for all results for the parameter with a PCI value for a subject, including the subject number, site, baseline, and post-baseline values.

	Parameter	Unit	Lower Limit	Upper Limit
Chemistry	Albumin	g/L	<=20	>=90
	Alkaline Phosphatase	U/L	NA	>2*ULN
	ALT	U/L	NA	>3*ULN
	AST	U/L	NA	>3*ULN
	Bilirubin	µmol/L	NA	>2*ULN
	BUN	mmol/L	NA	>=10.7
	Chloride	mmol/L	<=80	>=125
	Creatinine	µmol/L	NA	>=177
	Glucose	mmol/L	<=1.7	>=13.9
	Gamma glutamyl transferase	U/L	NA	>=100
	Magnesium	mmol/L	<0.7	>1.4
	Phosphate (Phosphorus)	mmol/L	NA	>=2
	Potassium	mmol/L	<=2.5	>=6.5
	Sodium	mmol/L	<=120	>=165
	Uric acid	µmol/L	NA	>=624 (males)
		NA	>=505 (females)	
Hematology	Hematocrit	fraction of 1	<=0.37 (males)	>0.54 (males)
			<=0.32 (females)	NA (females)
	Hemoglobin	g/L	<=115 (males)	NA
			<=95 (females)	NA
	Platelets	x10E9/L	<=75	>=700
	RBC count	x10E12/L	<=2.5 (males)	NA
			<=2.0 (females)	NA
	WBC count	x10E9/L	<=2.8	>=16.0
Basophils/Leukocytes	L/L	NA	>=0.15	

	Parameter	Unit	Lower Limit	Upper Limit
	Eosinophils/Leukocytes	L/L	NA	$\geq 0.10$
	Lymphocytes/Leukocytes	L/L	NA	$\geq 0.80$
	Monocytes/Leukocytes	L/L	NA	$\geq 0.40$
	Neutrophils/Leukocytes	L/L	$\leq 0.15$	NA
24-Hour urine	Urine calcium	mg	NA	>300 for men
		mg	NA	>250 for women

Listings for serum and urinary clinical laboratory results will be produced for all patients in the Safety Analysis Set.

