**Table 1 Schedule of Assessments**

Study Visit	Screening		Predose Assessment		Treatment Period 1		Washout	Predose Assessment		Treatment Period 2		Follow-up
	Admin.	Clinical	TP1, D-2	TP1, D-1	TP1, D1	TP1, D2	W a,b	TP2, D-2	TP2, D-1	TP2, D1	TP2, D2	FU
Study Relative Day/ Study Procedures	-120 to -03	-28 to -03	-2	-1	1	2		-2	-1	1	2	Follow-up c
Withhold supplemental oral calcium and active vitamin D s					X t					X t		
Administration of supplemental oral calcium only (no active vitamin D) u					X v					X v		

HBsAg=hepatitis B surface antigen; HCV=hepatitis C virus; HIV=human immunodeficiency virus

a Washout period should be  $\geq 5$  days (ie, 120 hours) and  $\leq 30$  days between first dose of each treatment period (whether dosing regimen is BID or QD).

b The investigator may elect to keep the subject in-clinic for the duration of the study, if the washout period is short (eg, 120-172 hours) and/or there are any safety concerns, and provided that there is a minimum washout of  $\geq 120$  hours between administration of IP in each treatment period.

c A follow-up visit must be completed  $30 \pm 2$  days after the last dose of IP.

d If applicable.

e Review and update medical history and re-confirm eligibility.

f In the event a subject is prematurely discontinued from the study, every attempt should be made to complete these assessments.

g The safety blood and urine assessments (Period 1 and Period 2), pregnancy test (for all females, Period 2), physical exam (Period 2), and weight (Period 2) should be collected after the scheduled serial PK and PD assessments have been completed on this study day, and prior to discharging the subject from the Clinical Research Center.

h Randomization will occur prior to administration of IP at Treatment Period 1, Day 1 only after all eligibility criteria have been confirmed/re-confirmed.

i Vital sign measurements should be collected in the supine position at each time point.

j See Table 2, Table 3, and Table 4 for detailed collection time points.

k Weight measurement only.

l ECGs will be performed in triplicate measurement at each time point.

m Includes thyroid function tests, and estimated creatinine clearance (Cockcroft–Gault formula) at Clinical screening visit only.

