j The last scheduled serial time point (ie, 24 hours) will also serve as the discharge procedure for these assessments on Day 2.

k The urine sampling under predose in this table is to signify the stop of Day -1, 18-24 hour PD urine collection period, and the start of the Day 1, 0-3 hour PD urine collection period. It is not a separate predose collection.

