**Table 4: Detailed Schedule of Assessments: Treatment Periods 1 and 2, Day 1/Day 2 (BID Regimen)**

Study Day	1																						2					
Time point (relative to first dosing time on Day 1) (h=hour/m=minute)	Pre-dose	0	10m	20m	30m	1	1.5	2	4	6	8	10	Pre- dose (12hr)	12	12h 10m	12h 20m	12.5	13	13.5	14	16	18	20	22	24	28	32	36

a An attempt to perform these assessments and procedures should be made for any subject who withdraws or is removed from the study.

b Vital signs should be collected in the supine position at each time point. Subject should also be supine at least 5 minutes prior to vitals collection. Vital signs include blood pressure and pulse.

c These assessments should be performed within 30 minutes prior to the scheduled time for IP dose administration on Day 1.

d ECGs will be performed in triplicate measurement at each timepoint.

e Randomization will occur prior to administration of IP of Treatment Period 1, Day 1 only (and only after all eligibility criteria have been confirmed/re-confirmed).

f Pre-dose PK/PD collection for the second dose of the BID regimen should be completed within 15 minutes prior to the dose.

g PD blood sampling assessments will include: total serum calcium, magnesium, phosphate, albumin, creatinine, 1,25-dihydroxyvitamin D, and FGF23.

h The anti-PTH antibody sample should only be collected at Treatment Period 1, pre-dose (regardless of BID or QD regimen), and the sample collected within 30 minutes prior to dosing.

i 36-hour urine collection for PD analysis will be collected according to the following collection intervals: 0-3 hours, 3-6 hours, 6-9 hours, 9-12 hours, 12-15 hours, 15-18 hours, 18-24 hours, 24-30 hours, 30-36 hours. 'X' denotes the start and stop of the entire urine collection period and '→' denotes continuous collection.

j PD urine collection assessments will include: calcium, sodium, citrate, phosphate, magnesium, cAMP, and creatinine.

k The last scheduled serial time point (ie, 36 hour time point) will also serve as the discharge procedure for these assessments on Day 2.

l The urine sampling under pre-dose in this table is to signify the stop of Day -1, 18-24 hour PD urine collection period, and the start of the Day 1, 0-3 hour PD urine collection period. It is not a separate pre-dose collection.

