During Treatments A, B, and C (Cohorts 1 and 2), supplemental oral calcium and active vitamin D will be withheld starting on Day 1 (predose), through the completion of all study procedures on Day 2 for both the once-daily and twice-daily dosing regimens. Upon completion of all study procedures on Day 2, subjects will then resume their usual supplemental oral calcium and active vitamin D at their next usual daily schedule.

During Treatments D, E, and F (Cohorts 3 and 4), subjects will withhold active vitamin D on Day 1 but take their usual dose(s) of supplemental oral calcium according to their usual regimen, regardless of the schedule/timing of investigational product administration(s).

Critically, oral calcium supplementation should be identical on Day -1, Day 1 and Day 2 in Treatment Period 1 and Treatment Period 2. On Day 2, subjects will continue with their usual supplemental calcium regimen (ie, identical on Day -1 and Day 1), and, following the completion of all study procedures, subjects will then re-start their active vitamin D at their next usual daily schedule.

During the washout period, subjects will be instructed to take their usual doses of supplemental oral calcium and active vitamin D.

Any subject who experiences symptoms of hypocalcemia or hypercalcemia may be treated at the investigator's discretion, as per local standards. This may include, but is not limited to, intravenous (IV) calcium and/or fluids.

For all dosing regimens, rhPTH(1-84) will be administered in the morning of Day 1 of each treatment period following an overnight fast of at least 8 hours. Subjects will continue to fast until approximately 2 hours after rhPTH(1-84) administration, at which time a standardized meal will be served (see Section 4.3 item 5). For subjects assigned to the twice-daily dose regimen, the evening dose of investigational product will be administered 12 hours after the morning dose, and 2 hours prior to the evening meal. A snack or light meal may be provided to the subjects prior to the evening dose, provided it is consumed  $\geq 2$  hours prior to investigational product dose administration. It is suggested that lunch be divided into 2 portions, the first portion consumed at lunch, and the second portion consumed as the snack or light meal.

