i PD urine collection assessments will include: calcium, sodium, citrate, phosphate, magnesium, cAMP and creatinine.

j The last scheduled serial timepoint (i.e., 24 hours) will also serve as the discharge procedure for these assessments on Day 2.

k The urine sampling under pre-dose in this table is to signify the stop of Day -1, 18-24 hour PD urine collection period, and the start of the Day 1, 0-3 hour PD urine collection period. It is not a separate pre-dose collection.

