**Table 4: Detailed Schedule of Assessments: Treatment Periods 1 and 2, Day 1/Day 2 (BID Regimen)**

Study Day	1																						2					
Time point (relative to first dosing time on Day 1) (h=hour/m=minute)	Pre- dose	0	10m	20m	30m	1	1.5	2	4	6	8	10	Pre- dose (12hr)	12	12h 10m	12h 20m	12.5	13	13.5	14	16	18	20	22	24	28	32	36

i 36- hour urine collection for PD analysis will be collected according to the following collection intervals: 0-3 hours, 3-6 hours, 6-9 hours, 9-12 hours, 12-15 hours, 15-18 hours, 18-24 hours, 24-30 hours, 30-36 hours. ‘X’ denotes the start and stop of the entire urine collection period and ‘→’ denotes continuous collection.

j PD urine collection assessments will include: calcium, sodium, citrate, phosphate, magnesium, cAMP and creatinine.

k The last scheduled serial timepoint (i.e., 36 hour timepoint) will also serve as the discharge procedure for these assessments on Day 2.

l The urine sampling under pre-dose in this table is to signify the stop of Day -1, 18-24 hour PD urine collection period, and the start of the Day 1, 0-3 hour PD urine collection period. It is not a separate pre-dose collection.

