## 11.4 Electrocardiogram (ECG)

At each timepoint, ECGs are collected in triplicate (any readings after the first three valid readings at a particular timepoint will be considered unscheduled). For numeric ECG variables, the mean of the valid values at each timepoint will be taken. For qualitative ECG results, the worst case will be used. Baseline for numeric ECG results is the mean of the available valid values at the last timepoint with any non-missing data prior to the first dose of investigational product in that period. For qualitative ECG results, baseline will be the worst case at the last timepoint with any non-missing data prior to the first dose of investigational product in that period.

Descriptive statistics for ECG variables (eg, heart rate, PR interval, QRS interval, QT interval, and QTc interval) and their changes from baseline at each assessment time point will be presented by treatment. QTc interval will be calculated using both Bazett ( $QTcB=QT/(RR)^{1/2}$ ) and Fridericia ( $QTcF=QT/(RR)^{1/3}$ ) corrections; and if RR is not available, it will be replaced with 60/hr in the correction formula. ECG interpretation will be summarized by visit. A shift table from baseline to each timepoint for qualitative ECG results will be presented. All ECG results will be listed for each subject in the Safety Analysis Set.

Electrocardiogram variable values will be considered PCI if they meet or exceed the upper limit values listed in [Table 7](#). Assessment of whether a value is PCI will be based on the derived average at each timepoint for each subject. The number and percentage of subjects with post-baseline PCI values will be tabulated by treatment. The percentages will be calculated relative to the number of subjects with available non-PCI baseline and at least 1 post-baseline assessment. The numerator is the total number of subjects with at least 1 PCI post-baseline ECG value. A listing of all subjects with post-baseline PCI value will be provided including the subject number, site, baseline, and post-baseline PCI values.

Table 7: Criteria for Potentially Clinically Important ECG Values	
Parameter	Upper Limit
QTcB	> 500 ms, > 480 ms, >450 ms
QTcF	> 500 ms, > 480 ms, >450 ms
QTcB	An increase from Baseline of $\geq 60$ ms and $\geq 30$ ms
QTcF	An increase from Baseline of $\geq 60$ ms and $\geq 30$ ms

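### By-treatment safety summaries compare QD and BID over unequal windows: Day 2 labs at about 24 h versus 36 h after first dose, and at-least-one flags over 14 versus 17 readings

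*SAP*

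**What the plan says.** **Laboratory tables.** SAP 11.2 gives descriptive statistics at each assessment time point and adds that "shift tables from baseline to each visit for quantitative variables will be presented by treatment". Protocol Table 1 has a single Day 2 column per period for biochemistry, hematology and urinalysis, with no hour. Its footnote g says these samples "should be collected after the scheduled serial PK and PD assessments have been completed on this study day".

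**When serial sampling ends.** For QD, Protocol Table 3 footnote j reads "The last scheduled serial time point (ie, 24 hours) will also serve as the discharge procedure". For BID, Protocol Table 4 footnote k reads "The last scheduled serial time point (ie, 36 hour time point) will also serve as the discharge procedure". The SAP's own schedules repeat both footnotes. They concern vital signs and ECG, but PK, PD and urine collection stop at the same hours.

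**Supplements.** Protocol 3.1 withholds oral calcium and active vitamin D in Treatments A-C from before the Day 1 dose "through the completion of all study procedures on Day 2 for both the once-daily and twice-daily dosing regimens". It withholds active vitamin D in every cohort until Day 2 procedures are complete, and keeps usual oral calcium going on Days 1 and 2 in Treatments D-F. Footnote t of Protocol Table 1, repeated in the SAP schedule, instead ends withholding in A-C at the end of Day 1.

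**Flags.** SAP 11.4 says of the PCI percentage: "The numerator is the total number of subjects with at least 1 PCI post-baseline ECG value". SAP 11.3 uses the same construction for vital signs. SAP 11.1 tabulates hypercalcemia, hypocalcemia and hypercalciuria as TEAEs of special interest by treatment, counting onsets up to 5 days after the last dose.

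**The concern.** Safety and tolerability is the secondary objective, and Protocol 2.1 frames the study as a comparison of twice-daily with once-daily dosing. With about 8 subjects per cohort and descriptive tables only, readers will compare the QD and BID columns directly. If the Day 2 row holds a morning 24 h value for QD and an evening 36 h value for BID, a difference in calcium, phosphorus, magnesium, creatinine or glucose could reflect clock time, elapsed time or supplement status rather than regimen. Any summary that counts subjects with at least one event also gives BID more time or more readings in which to register one. The crossover offers no protection, because the sampling time changes with the regimen within each subject.

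**Working it through.** **1. Timing of the Day 2 labs.** Inputs: first dose in the morning of Day 1 in both regimens; second BID dose 12 h later; serial sampling to 24 h after the last dose (Protocol 3.1, Tables 3 and 4).

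Last serial time = time of last dose + 24 h.

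- QD: 0 + 24 = 24 h after first dose.
- BID: 12 + 24 = 36 h after first dose.

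Both reproduce the figures in the footnotes. The documents fix no dosing hour. Assuming 07:00 to 10:00, the earliest lab draw on Day 2 is:

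| | QD | BID |
|---|---|---|
| Hours since first dose | 24 | 36 |
| Hours since last dose | 24 | 24 |
| Clock time | 07:00-10:00 | 19:00-22:00 |

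**2. Supplement status at the draw.**

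- *Body text:* withholding lasts at least 24 h (QD) or 36 h (BID), a difference of 36 - 24 = 12 h. In A-C this covers calcium and active vitamin D; in D-F it covers active vitamin D only.
- *Footnote t (A-C):* withholding ends at midnight, 24 - 10 = 14 h to 24 - 7 = 17 h after the dose in both regimens. The 12 h excess disappears. Resumption would be allowed from 7-10 h before the QD draw and 19-22 h before the BID draw, so BID subjects could already have resumed.

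The two passages imply different supplement states at the same draw. The exclusion rule in SAP 4.5 runs to 24 h after the last dose (36 h after first dose on BID), which matches the window in the body text but does not settle the conflict.

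**3. Chances to be flagged.** Scheduled post-dose ECG and vital-sign times:

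- QD: 1, 2, 4, 6, 8, 10, 12, 13, 14, 16, 18, 20, 22, 24 h = 14.
- BID: the same hours (12 h taken before the second dose) plus 28, 32 and 36 h = 17.

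Follow-up and unscheduled readings are not in these counts. The documents give no flag rate, so assume an independent rate p per reading. P(at least one) = 1 - (1 - p)^k.

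| p | k = 14 | k = 17 | Difference | Per 8 subjects |
|---|---|---|---|---|
| 1% | 13.1% | 15.7% | 2.6 points | 0.2 |
| 2% | 24.6% | 29.1% | 4.4 points (unrounded) | 0.4 |

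Readings within a subject are correlated, which narrows these gaps. Restricted to 0-24 h, the count is 14 in both regimens.

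**4. TEAE window.** Five days is 120 h after the last dose. From first dose that is 120 h (QD) and up to 12 + 120 = 132 h (BID), or 12/120 = 10% longer. It is cut short where Period 2 dosing comes first.

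**The case against.** The strongest reply is that the schedule already matches the interval that matters most pharmacologically: both Day 2 draws are 24 h after the last dose. That is true. It is also why the 24 h PD sample should not replace the Day 2 lab. At that sample BID is 12 h and QD 24 h after last dose, and Protocol 2.1 puts the maximum mean rise in serum calcium at 12 h after dosing. Substitution would exchange one mismatch for another.

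Other parts of the reply also stand:

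- The table list in SAP 20 titles the vital-sign and ECG PCI tables (4.7.2 and 4.8.4) as by timepoint. If they follow their titles, matched hours can be compared. The text of 11.3 and 11.4 still defines the percentage as at least one value over all post-baseline readings.
- Serial calcium, phosphate, magnesium and creatinine concentrations, including 24 h in both regimens, are already summarized by treatment (SAP 12.4.5). Serum calcium has no laboratory PCI limit.
- Table shells are in a separate document, so a shared Day 2 row is inferred from the schedule and the SAP wording. Treatments are in separate columns, not pooled.
- Over the full TEAE window the excess is only about 10%.

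A reader might infer that BID subjects always go 12 h longer without supplements and that this works against BID. The documents do not support that. Oral calcium continues in Cohorts 3 and 4, and under footnote t the excess in A-C vanishes and could reverse.

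**Conclusion.** The point holds as a modest defect of presentation. Day 2 laboratory values are tied to regimen through a 12 h difference in time since first dose and in clock time, and nothing in SAP 11.2 marks it. This follows from the schedule and depends on no assumed rate. The further 12 h difference in withholding is conditional on the body text of Protocol 3.1, differs by cohort, and cannot be given a direction in A-C until footnote t is reconciled with it. Unequal counting of ECG and vital-sign flags is real (17 versus 14) but probably worth less than half a subject in 8, on assumed independent rates of 1% to 2%.

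It would go too far to say that all safety tables are confounded. ECG and vital-sign summaries by time point have matched hours through 24 h. The analyses are descriptive, so no error rate is affected. What is at stake is a misreading of small by-treatment differences, and that can be prevented cheaply.

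**What to change.** - **SAP 11.2:** label Day 2 laboratory results with hours since first and last dose (24 h and 24 h for QD; 36 h and 24 h for BID) and with supplement status by treatment. Cross-refer to the 24 h PD values for calcium, phosphate, magnesium and creatinine as a clock-time-matched supplement, not a replacement. State that BID is then 12 h and QD 24 h after last dose.
- **SAP 11.1:** tabulate special-interest TEAEs by onset 0-24 h after first dose versus later, beside the full 5-day window. Note that under SAP 18.5.1 a Day 2 event with no recorded time is set to 00:00 and so falls in the 0-24 h group.
- **SAP 11.3 and 11.4:** give the at-least-one-PCI percentage for 0-24 h after first dose in both regimens, beside the full-window figure.
- **Protocol and SAP:** reconcile footnote t with the body text on withholding in A-C. Also reconcile SAP 2.1, which ties Day 1 calcium in D-F to the time before dosing, with the usual-regimen wording in Protocol 3.1. The supplement-status label depends on both.

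The statistical changes use data already collected and cost one extra column or row per table plus wording. The 0-24 h window has its own limit: it covers only 12 h after the second BID dose. Protocol 2.1 speaks of a 24-hour comparison and the synopsis of 24-36 hours, so showing both windows serves both.

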### 11.3 Vital Signs

Descriptive statistics for vital signs (eg, systolic and diastolic blood pressure, pulse rate, and body weight) and their changes from baseline at each post-baseline assessment and at the end of study will be presented by treatment. All vital signs will be listed for each subject in the Safety Analysis Set.

Vital sign values will be considered PCI if they if they meet either the low or high PCI criteria listed in [Table 6](#). The number and percentage of subjects with PCI post-baseline values will be tabulated by treatment. The percentages will be calculated relative to the number of subjects with baseline and at least 1 post-baseline assessment. The numerator is the total number of subjects with at least 1 PCI post-baseline vital sign value. A supportive listing of subjects with post-baseline PCI values will be provided including the subject number, site, baseline, and post-baseline PCI values.

Parameter	Unit	Lower Limit	Upper Limit
Systolic blood pressure	mmHg	A decrease from Baseline of $\geq 20$ to a value $\leq 90$	An increase from Baseline of $\geq 20$ to a value $\geq 180$
Diastolic blood pressure	mmHg	A decrease from Baseline of $\geq 15$ to a value $\leq 50$	An increase from Baseline of $\geq 15$ to a value $\geq 105$
Pulse rate	bpm	A decrease from Baseline of $\geq 15$ to a value $\leq 50$	An increase from Baseline of $\geq 15$ to a value $\geq 120$

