### **2.4 Schedule of Assessments**

### STUDY SCHEDULE(S)

**Table 2: Schedule of Assessments**

Study Visit	Screening		Predose Assessment		Treatment Period 1		Washout	Predose Assessment		Treatment Period 2		Follow-up
	Admin.	Clinical	TP1, D-2	TP1, D-1	TP1, D1	TP1, D2	W a,b	TP2, D-2	TP2, D-1	TP2, D1	TP2, D2	FU
Study Relative Day/ Study Procedures	-120 to -03	-28 to -03	-2	-1	1	2		-2	-1	1	2	Follow-up c
Informed consent	X d	X										
Medical record release	X d	X d										
Inclusion/exclusion criteria		X	X e	X e								
Demography and medical/medication history		X	X e									
Physical exam f		X		X e							X g	
Randomization					X h							
Vital signs (blood pressure, pulse) f,i,j		X		X	X	X			X	X	X	X
Height and weight f		X	X k								X k,g	
Electrocardiogram (12-lead) f,j,l		X		X	X	X			X	X	X	X
Biochemistry, hematology, and urinalysis f		X m	X			X g		X			X g	X
Serum 25(OH)D		X										
Anti-PTH antibody sampling f					X							X
HIV, HBsAg, and HCV screen		X										

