**Table 2: Schedule of Assessments**

Study Visit	Screening		Predose Assessment		Treatment Period 1		Washout	Predose Assessment		Treatment Period 2		Follow-up
	Admin.	Clinical	TP1, D-2	TP1, D-1	TP1, D1	TP1, D2	W a,b	TP2, D-2	TP2, D-1	TP2, D1	TP2, D2	FU
Study Relative Day/ Study Procedures	-120 to -03	-28 to -03	-2	-1	1	2		-2	-1	1	2	Follow-up c
medication t												
Administration of usual supplemental oral calcium and active vitamin D		X	X	X			X	X	X			X
Withhold supplemental oral calcium and active vitamin D s					X t					X t		
Administration of supplemental oral calcium only (no active vitamin D) u					X v					X v		

a Washout period should be ≥5 days (ie, 120 hours) and ≤30 days between first dose of each treatment period (whether dosing regimen is BID or QD).

b The investigator may elect to keep the subject in-clinic for the duration of the study, if the washout period is short (eg, 120-172 hours) and/or there are any safety concerns, and provided that there is a minimum washout of ≥120 hours between administration of IP in each treatment period.

c A follow-up visit must be completed 30±2 days after the last dose of IP.

d If applicable.

e Review and update medical history and re-confirm eligibility.

f In the event a subject is prematurely discontinued from the study, every attempt should be made to complete these assessments.

g The safety blood and urine assessments (Period 1 and Period 2), pregnancy test (for all females, Period 2), physical exam (Period 2), and weight (Period 2) should be collected after the scheduled serial PK and PD assessments have been completed on this study day, and prior to discharging the subject from the Clinical Research Center.

h Randomization will occur prior to administration of IP at Treatment Period 1, Day 1 only after all eligibility criteria have been confirmed/re-confirmed.

i Vital sign measurements should be collected in the supine position at each time point.

j See **Error! Not a valid bookmark self-reference.**, Table 3, and Table 4 for detailed collection time points.

k Weight measurement only.

l ECGs will be performed in triplicate measurement at each time point.

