## 11. SAFETY ANALYSES

The safety analysis will be performed using the Safety Analysis Set. Safety variables include AEs and TEAEs, clinical episodes of hypocalcemia and/or hypercalcemia, and hypercalciuria, clinical laboratory variables, vital signs, and ECG variables. For clinical laboratory and vital sign variables, the last value collected before the first dose of investigational product in that period will be used as baseline for all analyses of that safety variable in that period.

Assessments at the follow-up visit will be assigned to the last treatment the patient received. Early termination visits will be summarized separately, and assigned to the treatment in Period 1 if prior to first dose of investigational product in Period 2, and assigned to treatment in Period 2 if after the first dose of investigational product in Period 2.

For handling of unscheduled visits, refer to Section 18.

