### **18.3 Repeated or Unscheduled Assessments of Safety Parameters**

If a subject has repeated assessments before the start of investigational product, then the results from the final assessment made prior to the start of investigational product will be used as baseline. In addition to determination of baseline, unscheduled visits will be included in PCI value determination. However, for all other summaries only scheduled visits will be used.

All assessments (including unscheduled) will be presented in the data listings.

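### Body-weight change is to be shown by treatment, but the only scheduled change spans both regimens and the washout and falls under whichever regimen came second

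*SAP*

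**What the plan says.** SAP 11.3 (Vital Signs) plans "Descriptive statistics for vital signs (eg, systolic and diastolic blood pressure, pulse rate, and body weight) and their changes from baseline", and the same sentence goes on: "at each post-baseline assessment and at the end of study will be presented by treatment". Body weight is thus named alongside blood pressure and pulse, with no separate treatment.

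SAP 11 (Safety Analyses) fixes the baseline for laboratory and vital-sign variables in each period: "the last value collected before the first dose of investigational product in that period will be used as baseline". SAP 18.3 adds that, where assessments are repeated before dosing, "the results from the final assessment made prior to the start of investigational product will be used as baseline". Neither section makes an exception for weight.

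The row "Height and weight" in SAP Table 2 has entries at Clinical Screening, Period 1 Day -2 and Period 2 Day 2 only; the footnote to the last two reads "Weight measurement only". Protocol Table 1 has the same row. A further footnote fixes the timing of the last weight: "physical exam (Period 2), and weight (Period 2) should be collected after the scheduled serial PK and PD assessments have been completed". No weight is scheduled on Period 1 Day 2, during washout, on any day before the Period 2 dose, or at follow-up.

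**The concern.** A baseline specific to each period works for blood pressure, pulse and the safety laboratory tests, because these are measured before and after dosing in both periods. Weight is grouped with them but is measured once before either regimen and once after both. Applied to weight, the rule gives a column headed with one treatment whose content reflects two treatments and the interval between them, and about half of each treatment's subjects are absent for reasons of schedule alone.

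Within a cohort the comparison of columns would mislead. In Cohort 1, column A would hold only subjects who took B and then A, and column B only those who took A and then B. Everyone in both columns received both regimens, so any difference between the columns reflects order and not treatment. Nothing in the SAP would warn a reader of this.

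**Working it through.** The plan states no figure on this point, so there is none to reproduce. The check sets the schedule against the baseline rule and then counts days and subjects.

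**Inputs**
- Weights: Clinical Screening, Period 1 Day -2, Period 2 Day 2 (SAP Table 2; protocol Table 1).
- Time between periods: "Washout period should be ≥5 days (ie, 120 hours) and ≤30 days between first dose of each treatment period" (SAP Table 2, footnote a).
- Day numbering: there is no Day 0 (SAP 12.3.3), so Day -2 to Day 1 is 2 days.
- Planned numbers: 4 subjects per sequence, 2 sequences per cohort, 4 cohorts (SAP Table 1).

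**Which change exists**
1. Period 1 regimen: the baseline is Period 1 Day -2. There is no scheduled weight between the Period 1 dose and the Period 2 dose, so no change can be formed.
2. Period 2 regimen: the last scheduled weight before the first Period 2 dose is again Period 1 Day -2. The only post-dose weight is Period 2 Day 2.
3. A completer therefore has one weight change, from Period 1 Day -2 to Period 2 Day 2, and it falls in Period 2.

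**Length of the interval**

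Interval = (Day -2 to Day 1) + (first dose to first dose) + (Day 1 to Day 2)
- Shortest: 2 + 5 + 1 = 8 days
- Longest: 2 + 30 + 1 = 33 days

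Time after the first Period 2 dose, as a share of the interval:
- Once-daily regimen second (about 1 day): 1/8 = 12.5% down to 1/33 = 3.0%
- Twice-daily regimen second (36-hour schedule, so 1.5 days and an interval of 8.5 to 33.5 days): 1.5/8.5 = 17.6% down to 1.5/33.5 = 4.5%

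**Subjects with a value**

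| Treatment | Receive it | Receive it second (have a weight change) |
|---|---|---|
| A, C, D, F (each) | 4 + 4 = 8 | 4 |
| B, E (each; two cohorts) | 2 × 8 = 16 | 2 × 4 = 8 |

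**Comparison within the SAP**

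Anti-PTH antibodies have the same sampling shape: once before the Period 1 dose and once at follow-up, after both regimens. SAP 11.5 summarizes them for all subjects together, not by treatment. SAP 11.2 likewise keeps laboratory tests done only at screening out of the summary tables and lists them. The SAP therefore already fits its displays to the schedule elsewhere.

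**The case against.** The strongest objection is that attribution to the second regimen is inferred. SAP 11 does not say that a Period 1 pre-dose weight carries over as the Period 2 baseline. If each period needs a baseline from its own admission, nothing is misattributed and the cell is simply empty. That reading is possible, but it leaves the planned summary impossible to compute, so the text needs changing either way.

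The end-of-study clause in SAP 11.3 could be read as covering the Period 2 Day 2 weight. That summary is also by treatment, so the difficulty remains. SAP 11 does openly assign follow-up assessments to the last treatment received, but no weight is scheduled at follow-up.

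The table shells are in a separate document that is not available here. The title of Table 4.7.1 in SAP Section 20 does not name weight, and the protocol's schedules list vital signs as blood pressure and pulse. Whether the shell has a weight-change row cannot be confirmed, but SAP 11.3 names body weight explicitly and is the text the table has to implement.

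Other sources of weights do not rescue the row. A subject who stops early may be weighed in Period 1, but SAP 11 summarizes early termination visits separately. Under SAP 18.3 unscheduled values count only towards baseline and the determination of potentially clinically important values, and no extra weight is planned.

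The point about consequence stands in full. Weight has no potentially clinically important limit in SAP 11.3, is not named among the safety evaluations in protocol 9.9, and is subject to no test. The reduced n would be visible, and individual values are listed.

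**Conclusion.** The concern holds. As written, SAP 11 and 11.3 produce a by-treatment weight change that does not describe the treatment it is filed under: it spans 8 to 33 days and both regimens, and is available for half of each treatment's subjects. This rests on completers, the scheduled visits, the planned 4 per sequence, and a literal reading of the baseline rule. Under the stricter reading the row is uncomputable rather than misleading. The matter is minor: no objective, hypothesis or safety-review decision depends on it.

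**What to change.** In SAP 11.3, state that weight change is not summarized by treatment. Report one overall row, Period 1 Day -2 to Period 2 Day 2 for all subjects, and keep the by-subject listing. Make the same change to Table 4.7.1 and its shell. This follows the convention of SAP 11.5. A summary by sequence over the same interval would also be sound.

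The cost is a few words and one table row, with no new measurement. If a weight change for each regimen were wanted, weights at Period 1 Day 2 and Period 2 Day -2 would have to be added to the schedule; little in the plan suggests that is needed.
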